6.10 Assessment of Endpoints

The primary objective of the study is to demonstrate the safety and efficacy of allogeneic islet transplantation in improving glycemic control in Type 1 diabetic patients performed at the University of Illinois at Chicago.

6.10.1 Safety

Safety of islet cell transplantation in Type 1 diabetes depends primarily on determining the incidence of serious and unexpected complications or adverse events. Additionally, the ability of the cell isolation laboratory to produce uncontaminated islet cell preparations with minimal endotoxin content will be considered as a safety variable. The surgical implantation procedure has associated risk and complications of the islet cell infusion will be followed closely. The post-transplant immunosuppression regimen also has expected toxicities, both acute and chronic. Laboratory measures and signs and symptoms will be followed at specified intervals (see Section 6.6.8 *Schedule of Evaluation* and Appendix *Detailed Visit Schedule*). Some of these measures are often more subjective and variable in nature, but should provide a clear indication of relative safety for subjects enrolled in this study.

All study participants who receive an islet cell transplant will be followed for safety for 1 year following the last transplantation. The safety of the islet transplantation and associated immunosuppressive therapies will be evaluated by analysis of adverse experiences, clinical laboratory tests, and physical examination. Safety events will be analyzed by their incidence, severity, and relationship to islet cell transplantation. In particular, the following parameters are of primary interest in assessing the clinical safety of islet cell transplantation:

Specification of Safety Parameters

One year after first and the last islet transplants we will evaluate:

- a. Procedure Related Events
The incidence and severity of adverse events related to the islet infusion procedure including:
 - Bleeding (> 2 g/dl decrease in hemoglobin concentration)
 - Portal vein thrombosis, branch or main
 - Biliary puncture
 - Wound complication (infection or subsequent hernia)
 - Increased transaminase levels (> 5 times upper level of normal)
- b. Immunosuppression Related Events

The incidence and severity of adverse events related to immunosuppression including allergy:

- Reduction in GFR (> 25% reduction in estimated GFR from baseline by Cockcroft and Gault formula)
- Increase in urinary albumin excretion
- New onset microalbuminuria (albumin > 30 mg/day confirmed by 24 hour urine collection) in patients who were previously within normal limits
- For those patients with baseline microalbuminuria (30-300 mg/day), new onset overt albuminuria (greater than 300 mg/day confirmed by 24 hour urine collection)
- Addition or intensification of antihypertensive therapy
- Oral ulcers
- Lower extremity edema
- Gastrointestinal toxicity (diarrhea)
- Neutropenia (neutrophils < 1.3 thous/ μ L)
- Anemia (hemoglobin men < 12.1, women < 11.7 g/dL)
- Thrombocytopenia (platelets < 150 thous/ μ L)
- Infections (viral, bacterial, or fungal)
- Neoplasms, benign or malignant

Severity will be graded according to Collaborative Islet Transplant Consortium *Terminology Criteria for Adverse Events (TCAE) In Trials of Adult Pancreatic Islet Transplantation, Version 5.0 (03 August 2011)*

c. Islet Preparations for Transplant

The following parameters will be assessed to determine the safety of each islet preparation for transplant:

- Microbial contamination (preliminary Gram stain and subsequent culture results)
- Endotoxin content
- Final packed cell volume (mL)

A copy of the islet release sheet containing all the relevant information on the islet graft characteristics, unique batch identification number, and compliance with the release criteria will be included in the case report form.

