**** Alternative immunosuppressant trough level only if applicable**

5-Year Follow-Up

Subjects who complete the original 52-week post-transplant evaluation period will be asked to continue follow-up evaluations every three months for five years for safety and efficacy monitoring. All subjects can voluntarily withdraw from follow-up at any time.

The following examinations and blood tests will be performed according to the *Schedule of 5-Year Follow-Up* (Section 6.7.1). Additional evaluations may be required for medical conditions presenting during the study period and according to best medical practice. Should the function of the islet graft decline over time and the subject return to insulin therapy, repeat transplant may be considered.

- History and adverse event and toxicity assessments (reviewed at each visit and recorded at any time necessary)
- Physical exam including vital signs (blood pressure, heart rate, respiratory rate, temperature)
- Body mass index (BMI, body weight in kilograms over square of height in centimeters)
- Electrocardiogram (ECG)
- Comprehensive metabolic profile (CMP):
 - Na⁺, K⁺, Cl⁻, Ca⁺⁺, CO₂, creatinine, BUN, glucose, total protein, albumin, total bilirubin, ALP, AST, ALT, amylase
- Complete blood count (CBC):
 - Hemoglobin, hematocrit, red blood cells, white blood cells, differential
- Urine analyses
 - Urinalysis
 - Creatinine, osmolality, microalbumin, total protein
 - Microalbumin-creatinine ratio)
- Drug levels
 - Tacrolimus and sirolimus, and alternative trough levels if applicable to reach target levels as defined in Section 6.5.2
- Cytomegalovirus (CMV) viral load by real time PCR
- Epstein-Barr Virus (EBV) viral load by real time PCR
- HbA1c, basal C-peptide, fructosamine
- Blood sugar self-monitoring (BS-SM)
- Metabolic tests to evaluate insulin-secretory capacity of the islet graft:
 - IVGTT – intravenous glucose tolerance test
 - GST - glucagon stimulation test
 - OGTT – oral glucose tolerance test
 - MMTT - mixed meal tolerance test
- Detailed lipid panel:
 - Total cholesterol, direct LDL cholesterol, HDL cholesterol, triglycerides, apolipoprotein B, apolipoprotein A1, free fatty acids, and lipid fraction ratio
- Lipid panel:
 - Cholesterol, HDL, triglycerides, LDL cholesterol
- Inflammatory panel:

- CRP, MCP, MMP9, CAM, VCAM, fibrinogen, PAI-1 (antigen), TPA
- B-type natriuretic protein (BNP)
- Panel reactive antibodies (PRA)
- Antibodies: anti-GAD 65, anti-IA2, anti-islet cell, and anti-insulin

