## **2.6. Duration of Treatment**

The study duration will be approximately 10 years. The study will consist of a Screening/Baseline Phase, a Treatment Phase, and a Follow-up Phase. The Screening/Baseline Phase will consist of clinical and laboratory evaluations done at the first screening and repeated every 3 months (or 6 months for some, if needed) during the period awaiting the first transplant. The Treatment Phase will consist of Immediate Pre-Transplant Work-up, Transplant Period and Early Post-Transplant Period, all of which span from the moment a patient is admitted to the transplant unit up to when he/she is discharged after transplant, per protocol. Patients will remain in-clinic for a minimum of 24 hours post-transplant until the protocol-defined discharge criteria are met during the Treatment Phase. The Follow-up Phase includes continuous in-home monitoring of glucose levels and scheduled clinic visits that occur on an outpatient basis and will consist of efficacy and safety assessments for a period of 52 weeks post-transplant, followed by additional follow-up for up to 10 years (see Section 17.1 Schedule of Assessments for details). Individual patients will receive one or more transplants as needed as pre-determined by protocol and will be evaluated for efficacy and monitored for safety for up to 10 years following the last transplant.

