## **2.7. Criteria for Evaluation**

### **2.7.1 Safety:**

Safety assessments will be performed during the Screening/Baseline Phase, prior to and following the islet cell transplant during the Treatment Phase (at specified times), and during the Follow-up Phase.

Safety of islet cell transplantation in Type 1 diabetes depends primarily on determining the incidence of serious and unexpected complications or adverse events. The surgical implantation procedure has associated risk and complications of the islet cell infusion will be followed closely. The post-transplant immunosuppression regimen also has expected toxicities, both acute and chronic. Laboratory measures and signs and symptoms will be followed at specified intervals. Some of these measures are often more subjective and

variable in nature, but should provide a clear indication of relative safety for patients enrolled in this study.

All study participants who receive an islet cell transplant will be followed for safety up to 1 year following the last transplantation or up to the data cut-off date, 13 April 2015. The safety of the islet transplantation and associated immunosuppressive therapies will be evaluated by analysis of adverse experiences, clinical laboratory tests, and physical examination. Safety events will be analyzed by their incidence, severity, and relationship to islet cell transplantation. In particular, the following parameters are of primary interest in assessing the clinical safety of islet cell transplantation:

One year after first and the last islet transplants we will evaluate:

a. Procedure Related Events

The incidence and severity of adverse events related to the islet infusion procedure including:

- Bleeding (> 2 g/dl decrease in hemoglobin concentration)
- Portal vein thrombosis, branch or main
- Biliary puncture
- Wound complication (infection or subsequent hernia)
- Increased transaminase levels (> 5 times upper level of normal)

b. Immunosuppression Related Events

The incidence and severity of adverse events related to immunosuppression including allergy:

- Reduction in GFR (> 25% reduction in estimated GFR from baseline by Cockcroft and Gault formula)
- Increase in urinary albumin excretion
  - New onset microalbuminuria (albumin > 30 mg/day confirmed by 24 hour urine collection) in patients who were previously within normal limits

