## **10. SAFETY EVALUATIONS**

Safety analyses will be conducted for the Safety Population. Summaries will be prepared for the targeted safety endpoints listed below and for all observed adverse events (AE). All patients in the Safety population will be analyzed for safety endpoints for 1 year after the first and the last transplantation (if applicable) or up to the data cut-off date, 13 April 2015.

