#### **10.1.1. Definitions**

The following definitions will be applied consistently to the safety analysis:

Baseline (Clinical Labs, Physical Examinations)	The baseline value will be the result collected at the immediate pre-transplant work-up visit, if scheduled, or the most recent screening visit prior to the islet transplant where the lab/examination was scheduled.
Baseline (Vital Signs)	The baseline value will be the result collected at the immediate pre-transplant work-up visit. If this assessment was not obtained, then the most recent value obtained for

	the specific parameter prior to the islet infusion will be used as the baseline value.
Baseline (ECG parameters)	The baseline value will be the most recent pre-transplant value obtained.
Change from baseline	Value at the time point – value at baseline
Treatment-emergent	Any safety assessment that occurred at the onset of or after start of the first islet infusion, up to the end of 1-year follow-up after the last infusion.

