#### 10.1.5. Analyses of Adverse Events

Adverse events will be coded to the Medical Dictionary for Regulatory Activities (MedDRA) preferred terms (PT) and system organ classes (SOC) using version 17.0 or higher. All tabular AE summaries will be for treatment-emergent adverse events (TEAE). For all percentages, the number of patients in the ITT population will comprise the denominator.

An overall summary table will be developed to report, across the total safety population and by number of transplants received, starting from the day of first islet cells infusion to the end of 1-year follow-up after the last transplant, the total number of events and the number and percent of patients having at least one event and those related to treatment in the following categories:

a. Procedure Related Events

The incidence and severity of adverse events related to the islet infusion procedure including:

- Bleeding (> 2 g/dl decrease in hemoglobin concentration) identified within 24 hours post transplant.

- Portal vein thrombosis, branch or main, detected by ultrasound by the end of Day 7 (or on the first visit post-transplant if it does not fall on Day 7 exactly).
- Biliary puncture identified within 24 hours post transplant.
- Wound complication (infection or subsequent hernia) identified by the end of Day 7 (or on the first post-transplant visit if it does not fall on Day 7 exactly).
- Increased transaminase levels (> 5 times upper level of normal) identified by the end of Day 30 (or on the post-transplant visit that is closest to Day 30 if it does not fall on Day 30 exactly).

b. Immunosuppression/study drug Related Events

The incidence and severity of adverse events related to immunosuppression and/or the study drug (islets), including:

- Allergy
- Reduction in GFR (> 25% reduction in estimated GFR from baseline by Cockcroft and Gault formula:

$$eC_{Cr} = \frac{(140 - \text{Age}) \times (\text{Weight in kilograms}) \times [0.85 \text{ if Female}]}{72 \times (\text{Serum Creatinine in mg/dL})}$$

- Increase in urinary albumin excretion
- New onset microalbuminuria (albumin > 30 mg/day confirmed by 24 hour urine collection) in patients who were previously within normal limits
- For those patients with baseline microalbuminuria (30-300 mg/day), new onset overt albuminuria (greater than 300 mg/day confirmed by 24 hour urine collection)
- Sensitization evidenced by increase in PRA by at least 20% relative to baseline

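### No planned AE incidence table counts deaths, SAEs or neoplasms that occur more than 1 year after the last infusion, although adverse events are still collected in the optional 5- and 10-year follow-up

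*Protocol*

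**What the plan says.** **Where the safety analysis stops.** Protocol 6.10.1 states: "All study participants who receive an islet cell transplant will be followed for safety for 1 year following the last transplantation". SAP 2.7.1 has participants "followed for safety up to 1 year following the last transplantation or up to the data cut-off date, 13 April 2015", and SAP 10 analyses the Safety population "for safety endpoints for 1 year after the first and the last transplantation (if applicable) or up to the data cut-off date". SAP 10.1.1 defines treatment-emergent as running from the first infusion "up to the end of 1-year follow-up after the last infusion". SAP 10.1.5 adds: "All tabular AE summaries will be for treatment-emergent adverse events (TEAE". The last paragraph of 10.1.5 restricts the SAE and discontinuation listings in the same way.

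**Where collection stops.** After the 52-week period, the protocol's 5-Year Follow-Up section asks patients to "continue follow-up evaluations every three months for five years for safety and efficacy monitoring". Section 6.7 asks them to continue for five more years. Both sections include AE and toxicity review at each visit, and both schedules (6.6.9 and 6.7.1) list tacrolimus and sirolimus at every visit. Protocol 6.9.5 records SAEs with no time limit relative to transplantation. SAP 2.6 says patients "will be evaluated for efficacy and monitored for safety for up to 10 years following the last transplant".

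**What is of primary interest.** Protocol 6.10.1 names, among the immunosuppression-related events, a GFR reduction above 25% and "Neoplasms, benign or malignant".

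**The concern.** Safety is part of the primary objective, and both documents say that the series is meant to support a licence application. The protocol describes the toxicity of immunosuppression as both acute and chronic, says in 9.2.2 that such agents increase the risk of certain malignancies, and schedules cancer screening and thyroid ultrasound throughout the long-term follow-up. A neoplasm found at one of those visits, or a death or SAE in that period, is the kind of event the extended follow-up exists to detect. Under the SAP's rules it would contribute to no reported incidence.

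The documents also disagree on how long safety is followed. Protocol 6.10.1 and SAP 2.7.1 and 10 say one year. SAP 2.6 and the two long-term follow-up sections say much longer.

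**Working it through.** The plan gives no figure to reproduce on this point. The check is to trace each safety output to its time window.

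| Output | Window in the SAP |
|---|---|
| AE tables 14.3.1 to 14.3.5 | Treatment-emergent events only (10.1.5); the footnote to the Total column ends it at 1 year after the last transplant |
| SAE and discontinuation listings (14.3.6, 14.3.7) | Treatment-emergent, by the last paragraph of 10.1.5 |
| Listing for patients who died | Triggered by any death in the study, but its content is treatment-emergent events |
| Disposition, including death (14.1.1) | 1 year after last transplant or cut-off, whichever came first |
| ECG worsening | Assessment closest to Day 365 ± 28 after the last transplant (10.4.2) |
| Laboratory summaries, including creatinine and eGFR (14.3.13) | Each follow-up visit (10.3), with no treatment-emergent restriction |
| Per-patient listings (3.1; 16.2.1a, 16.2.1b, 16.2.7a) | No stated end |

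1. No AE incidence table reaches beyond one year after the last infusion, and no table in SAP 12.3 is dedicated to the later period.

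2. A late death, SAE or neoplasm could appear in the general listings, but with no incidence and no denominator.

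3. Late renal values are ambiguous. SAP 2.6 lets the follow-up phase run for up to 10 years, so each follow-up visit in 10.3 could include late visits. SAP 10 caps safety endpoints at one year. The GFR-reduction event in 10.1.5 falls under the treatment-emergent rule either way.

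4. The reference to the data cut-off in SAP 2.7.1 and 10 does not extend the window. The definition in 10.1.1 and the table footnotes stop at one year, and Table 14.1.1 takes whichever date came first.

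5. The time left out of the AE tables, by schedule, is 20 quarterly visits (20 × 3 = 60 months) in the 5-year follow-up and 20 more in the 10-year follow-up. By the cut-off, only patients last infused before about 13 April 2014 (13 April 2015 minus one year) could have any such time. Infusion dates and patient-years are not given, so neither the patients nor the events affected can be counted.

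6. Is the 1-year incidence biased? Assume a constant neoplasm hazard h of 1% per patient-year (range 0.5% to 2%; the documents give no rate). The 1-year risk is 1 − exp(−h) = 1.0% (0.5% to 2.0%), and the 6-year risk is 1 − exp(−6h) = 5.8% (3.0% to 11.3%). These are different quantities. The first is a correct 1-year figure and says nothing directly about later years.

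**The case against.** The strongest defence is that the plan is coherent. Protocol 6.10.1 evaluates its safety parameters one year after the first and last transplants, and the table footnotes state the window. Protocol 6.8.3 calls one year the scheduled minimum, and 6.10.3 says a 5-year follow-up will be offered. A mandatory year followed by a voluntary extension is a reasonable design. SAEs are recorded without time limit, the DMC meets every 3 months, and SAP 1 allows supplementary analyses in the report. Much of this stands: the 1-year tables are legitimate and should stay. But 6.10.1 and SAP 2.7.1 and 10 do not call the year a minimum, and a possible post-hoc analysis is not a planned one.

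Three stronger readings are tempting and are not supported:

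- **That known late events are being dropped or incidence understated.** The documents show that collection is planned, not that late events exist. Long-term follow-up is voluntary, and a 1-year incidence labelled as such is incomplete, not biased.
- **That late events would appear only in AE listing 16.2.7a.** The discontinuation and disposition listings in SAP 13.1 state no window, and the laboratory summaries may extend further. SAP 10.1.5 also names SAEs without qualification among its overall summaries, although its opening rule and the table row for serious TEAEs point to the 1-year limit.
- **That about 83% of first neoplasms fall outside the tables, or that they cover only 9% of follow-up.** The first is close to 5/6 and follows from an assumed constant hazard with six complete years. The second is 1/11, from reading the protocol's schedules end to end (1 + 5 + 5 years), while SAP 2.6 says up to 10. Nothing shows that any patient had such follow-up by 13 April 2015.

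Nor does every patient stay on immunosuppression. Protocol 6.8 lets subjects stop, and 6.5.2 ties mycophenolate to graft function.

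**Conclusion.** The point holds as a gap in what is summarised. As written, no AE incidence table can include a death, SAE or neoplasm more than one year after the last infusion, even one recorded before the cut-off. This rests on the SAP's own definition and tabulation rule. The loss is longer-term safety information that bears on the primary objective. It is not a bias in the 1-year figures. Its size for this report is unknown and may be small if few patients had passed one year. Coverage is also uneven: Protocol 6.5.1 allows a further infusion during the 5-year follow-up, which extends the window for those patients only. The change is worth making because it is cheap.

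**What to change.** - Keep the 1-year treatment-emergent tables unchanged.
- Add one supplementary table and one listing covering deaths, SAEs, neoplasms, serious infections and GFR loss above 25%, from first infusion to the earlier of last contact or 13 April 2015. For each event type give the number of patients with a first event (d), patient-years to first event or end of observation (T), the rate d/T and its exact Poisson 95% interval: lower limit χ²(0.025; 2d)/(2T), taken as 0 when d = 0, and upper limit χ²(0.975; 2d + 2)/(2T).
- State beside the table that late follow-up is voluntary and self-selected, that patient-years may mix time on and off immunosuppression, and that re-infusion during the 5-year follow-up lengthens some patients' treatment-emergent window.
- Amend Protocol 6.10.1 and SAP 2.7.1 and 10 to say that one year is the minimum follow-up and the treatment-emergent window. They would then agree with the 5-Year Follow-Up section, Protocol 6.7, 6.8.3 and 6.10.3, and SAP 2.6. Say which visits SAP 10.3 summarises.

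The cost is SAP and protocol wording plus one table and one listing, from data the protocol already provides for. No clinical rule and no new data collection is involved. The downside is that reported counts may rise, and late events are harder to attribute to the transplant or the drugs.

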6.10.2 Efficacy

Specification of Efficacy Parameters

a. Primary Efficacy Endpoint:

The proportion of subjects with an HbA1c \leq 6.5% and free of severe hypoglycemic events at 1 year after the first islet cell infusion

Standard insulin treatment can rarely improve glycemic control in brittle Type 1 diabetic patients who are already on state-of-the-art insulin therapy. In general these patients require insulin reduction to reduce hypoglycemic episodes, which would likely lead to higher HbA1c. In contrast, islet transplantation can reduce hypoglycemic episodes without increasing HbA1c.

Definition of severe hypoglycemic event: An event with symptoms compatible with hypoglycemia in which the subject required the assistance of another person and which was associated with either a blood glucose level < 50 mg/dl (2.8 mmol/L) or prompt recovery after oral carbohydrate, intravenous glucose, or glucagon administration.

For the primary endpoint (composite HbA1c \leq 6.5% and absence of severe hypoglycemic events), we expect 80% of the transplant population to achieve this endpoint. Therefore, assuming a sample size of 50, a two-sided 95.0% confidence interval for a single proportion will extend \pm 0.111 from the observed proportion. When the sample size is 40, a two-sided 95.0% confidence interval for a single proportion will extend \pm 0.124 from the observed proportion. Proportion and surrounding confidence interval will be reported.

Figure 2. Sample Size Curve for 95% Confidence Interval for Proportion

[figure not shown]
[figure not shown]

Figure 3 illustrates the cumulative percent of patients achieving HbA1c reduction from baseline in Phase1/2. As shown, all patients experienced a reduction in HbA1c (decrease of 0.6 to 2.7%). Furthermore, all patients presented with a HbA1c \leq 6.5 one year after final transplant.

Figure 3. Cumulative Percent of Patients Attaining HbA1c Reduction from Baseline at 1 Year after Last Transplant (N=7).

b. Secondary Efficacy Endpoints:

The secondary efficacy endpoints will focus on more detailed analysis of glycemic control, and will include the following:

1. **Insulin independence:** We will evaluate the proportion of subjects presenting with insulin independence while fulfilling the primary endpoint.

Definition of insulin-independence:

- Absence of exogenous insulin injection
- HbA1c \leq 6.5%
- Fasting capillary glucose level should not exceed 140 mg/dL (7.8 mmol/L) more than three times in the past week (based on measuring capillary glucose levels a minimum of 7 times in a seven day period).
- Fasting plasma glucose level \leq 126 mg/dL (7.0 mmol/L); if the fasting plasma glucose level is $>$ 126 mg/dL (7.0 mmol/L), it must be confirmed in an additional one out of two measurements.
- 2-hour postprandial capillary glucose should not exceed 180 mg/dl (10.0 mmol/L) more than three times in the past week

based on measuring capillary glucose levels a minimum of 21 times in a seven day period.

- Evidence of endogenous insulin production defined as fasting or stimulated C-peptide levels 0.5 ng/mL (0.16 nmol/L)
2. **Hypoglycemic episodes** will be measured by the number and severity of hypoglycemic episodes quantified by the Ryan HYPO Score (31) (see Appendix *HYPO Score sheets*), and the percent reduction will be reported.
 3. **Glucose variability and hypoglycemia duration will be measured by continuous glucose monitoring system (CGMS)** for a 3-day period at three different time points: 1) at screening, 2) one year after first islet transplant, and 3) one year after last islet transplant. The following measurements and analysis will be reported:
 1. Mean glucose concentration
 2. Percent of time in the following ranges:
 - < 60 mg/dl
 - 60-140 mg/dl
 - 141-200 mg/dl
 - > 200 mg/dl

